9.6. Data Management

The study will use an eCRF and all users will receive specific access codes to enable them to enter their data. The electronic data entry system will contain automatic checks for data completeness and to identify inconsistent data. Participating sites will enter available data from subject's medical records into the eCRF.

9.7. Data Analysis

Data will be analysed per arm. For categorical variables, numbers and percentages of patients will be reported including the according 95% confidence intervals.

For continuous variables, mean, standard deviation (SD), minimum, first and third quartile (Q1, Q3), median, and maximum will be calculated, together with the total number of observations and the number of missing values.

Missing values will not be imputed but classified as an own category to keep them for multivariate analyses.

Descriptive and multivariate data analysis will be done per treatment arm. Some cross arm comparisons according to sub groups (age \geq 50 years) might be conducted depending on group size.

Descriptive statistics will summarize demographics and baseline characteristics (including the type of regimen at enrollment).

The questionnaires scores will be calculated according to the algorithms elaborated for these questionnaires.

Visit windows will be defined (in the statistical analysis plan) to group data in order to generate descriptive statistics across time to assess potential trends in patient reported outcome questionnaires, safety data or CD4. P-values and/or confidence intervals (95% two-sided) will be calculated when considered relevant.

Multivariate analyses per arm (logistic regression) will be conducted to compare treatment naïve and non-naïve treatment groups adjusting for covariates. Longitudinal analysis will be done using mixed models.

Demographics and baseline measures would be potential confounders/effect modifiers for multivariate analyses. Confounders/effect modifiers and respective adjustments will be addressed in the Statistical Analysis Plan.

ADRs/SADRs and comorbidities will be coded using the Medical Dictionary for Regulatory Activities (MedDRA).

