8. RESEARCH QUESTIONS AND OBJECTIVES

To describe effectiveness, safety, adherence, resource utilization, and patient reported outcomes of E/C/F/TAF, F/TAF or R/F/TAF use in routine care.

The primary objective of this study is as follows:

- To evaluate HIV-1 RNA and CD4 cell count changes for patients using E/C/F/TAF, F/TAF or R/F/TAF within a time period of 24 months

The secondary objectives of this study are as follows:

- To describe rates of ADRs/SADRs for E/C/F/TAF, F/TAF and R/F/TAF
- To describe the motivation for ART initiation in treatment-naïve subjects (eg, early treatment according to guidelines, treatment as prevention, patient wish) and factors driving the ART switch to E/C/F/TAF, F/T/AF or R/F/TAF in treatment-experienced subjects (eg, simplification of ART, patient preference, side effects of current ART)
- To describe adherence (number of missed E/C/F/TAF, F/T/AF or R/F/TAF doses) and reasons for E/C/F/TAF, F/TAF or R/F/TAF discontinuation during the study
- To describe physical and mental health-related quality of life, health status, and treatment satisfaction using standardized questionnaires (Health Survey Short Form (SF-36), HIV Symptom Index, and HIV Treatment Satisfaction Questionnaire (only for treatment-experienced subjects))
- To describe health care resource utilization (eg, number of hospitalizations, number of physician visits)

The above parameters will be evaluated separately per treatment arm and in various subgroups (eg, treatment-naïve subjects versus treatment-experienced subjects, age (< 50 years, ≥ 50 years), presence of specific comorbidities, sex).

The collection of ADR/SADR reflects the real-life situation, in which the treating physician with best knowledge of his patient assesses whether an observed event could be related to a given treatment. In this way, the study will collect safety data that is reflective of the real-life setting in which it is conducted.

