9.3. Variables

Prior to E/C/F/TAF, F/TAF or R/F/TAF therapy initiation (baseline):

Gender, year of birth, body weight and height

Race

Date of HIV-1 diagnosis

CDC stage

Co-morbidities as available from medical records (eg, cardiovascular diseases, asthma, COPD, hypertension, hyperlipidemia, neuropsychiatric disorders, osteopathic disorder, diabetes mellitus, nephropathy, chronic hepatitis B, chronic hepatitis C)

Laboratory parameters as available from medical records:

- HIV-1 RNA and limit of detection of the used assay
- CD4 cell count
- AST, ALT, gamma-GT
- Albumin
- Urine albumin/creatinine ratio (UACR), urine protein/creatinine ratio (UPCR)
- Serum total protein
- Triglycerides
- Total cholesterol

- HDL, LDL
- Serum glucose
- Serum phosphate
- Serum creatinine
- Serum uric acid
- Blood urea nitrogen (BUN)
- Calcium, chloride, magnesium, potassium, sodium
- Urine dipstick parameters (glucose, leukocytes, nitrite, protein, pH, ketone bodies)
- Urine quantitative protein, albumin, and creatinine
- Hematology profile (complete blood count with differential and platelet count)
- Bone mineral density

History of anti-retroviral therapy

CD4 nadir

Blood pressure

Historic serum creatinine, quantitative urine creatinine, quantitative urine albumin, quantitative urine protein, and body weight within the last 2 years prior to E/C/F/TAF, F/TAF or R/F/TAF treatment initiation

Co-medications as available from medical records

Resistance status as available from medical records

Motivation for ART initiation in treatment-naïve subjects (eg, early treatment according to guidelines, treatment as prevention, patient wish) and factors driving the ART switch to E/C/F/TAF, F/TAF, or R/F/TAF in treatment-experienced subjects (eg, simplification of ART, patient preference, side effects of current ART)

Cardiovascular and renal risk factors (family history of angina/heart attack, smoking status, intravenous drug use, prior use of atazanvir, tenofovir disoproxil fumarate (TDF), indinavir or lopinavir)

HIV Symptom Index

HIV Treatment Satisfaction Questionnaire (only for treatment-experienced subjects)

SF-36

During follow-up (approximately 3 months, 6 months, 12 months, 18 months, and 24 months after starting E/C/F/TAF, F/TAF, or R/F/TAF therapy):

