9.9. Limitations of the Research Methods

As documentation of study variables is not obligatory missing data of unpredictable extent can occur.

Depending on the selection of sites selection bias cannot be excluded.

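### Making missing values their own category leaves residual confounding in naïve versus experienced comparisons that adjust for an incomplete confounder

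*Protocol*

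**What the plan says.** Section 9.7 (Data Analysis) of the protocol sets the rule without conditions: "Missing values will not be imputed but classified as an own category to keep them for multivariate analyses".

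The same section says where it will operate: "Multivariate analyses per arm (logistic regression) will be conducted to compare treatment naïve and non-naïve treatment groups adjusting for covariates". It adds for repeated measures: "Longitudinal analysis will be done using mixed models". On the adjustment set it says: "Demographics and baseline measures would be potential confounders/effect modifiers for multivariate analyses". What it leaves open is narrower: "Confounders/effect modifiers and respective adjustments will be addressed in the Statistical Analysis Plan". The choice of confounders is thus deferred to the SAP, but the handling of missing values is not. An SAP that used multiple imputation would contradict the protocol.

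Two other places show that incomplete covariates are foreseen. Section 9.3 collects the baseline panel, which includes HIV-1 RNA and CD4 count, under this heading: "Laboratory parameters as available from medical records". Section 9.9 concedes: "As documentation of study variables is not obligatory missing data of unpredictable extent can occur".

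**The concern.** The naïve and experienced groups within an arm are formed by treatment history, so they can be expected to differ in baseline HIV-1 RNA, CD4 count and other prognostic measures. Adjustment is meant to remove that difference. A missing category, or a missing indicator beside a continuous covariate, keeps every subject in the model. The price is that subjects with no recorded value are compared as if the covariate did not exist. The group coefficient then becomes a blend of an adjusted and a crude comparison.

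This does not depend on why the values are missing. It happens even when missingness is completely random, a case in which dropping the incomplete subjects would give no bias. The reported odds ratio, or mean difference, moves towards the crude value, and its confidence interval is centred in the wrong place.

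The sentence also speaks of missing values in general and does not say that it concerns covariates only. Section 8 makes HIV-1 RNA and CD4 change the primary objective, so the scope should be explicit.

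**Working it through.** **The plan's own figure.** There is none on this point. The protocol gives no missing rate, no imbalance between the groups and no confounder strength. All inputs below are assumptions, except the group size of about 150 naïve and 150 experienced subjects per arm (section 9.1).

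**Step 1: mechanism.** Let m be the share of subjects with a missing covariate, and let the true adjusted group odds ratio be 1.00. The observed stratum estimates log(1.00) = 0 and the missing stratum estimates log(crude OR). With weights roughly equal to the stratum shares:

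log(OR from the rule) ≈ (1 − m) × 0 + m × log(crude OR)

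For a crude OR of 1.65 to 1.70 (logs 0.501 and 0.531):
- m = 10%: exp(0.050) to exp(0.053), that is 1.05 to 1.06
- m = 30%: exp(0.150) to exp(0.159), that is 1.16 to 1.17

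**Step 2: simulation, continuous confounder.** Assumed: groups 0.8 SD apart, OR 2 per SD, true group OR 1.00, values missing completely at random, large samples. The crude OR is about 1.65 to 1.70.

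| Missing | Continuous covariate + missing indicator | Complete case |
|---|---|---|
| 10% | 1.06 to 1.07 | 0.99 to 1.01 |
| 30% | 1.18 to 1.20 | 0.99 to 1.01 |

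The simulated values lie slightly above the approximation in step 1.

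**Step 3: simulation, binary confounder.** Assumed: prevalence 0.6 in naïve and 0.2 in experienced subjects, true group OR 1.00, N = 1,000,000.

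| Missing | Rule, confounder OR 0.33 (crude about 0.63) | Rule, confounder OR 0.5 (crude about 0.75) |
|---|---|---|
| 0% | 1.01 | 1.00 |
| 10% | 0.95 | 0.97 |
| 20% | 0.89 | 0.94 |
| 30% | 0.85 | 0.91 |
| 50% | 0.78 | 0.85 |

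Complete-case adjustment stays at 0.99 to 1.01 throughout. The bias has the direction of the confounding, so here it is downward.

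**Step 4: when the bias disappears.** With nothing missing the rule gives about 1.00 (table above). With a balanced covariate and 30% missing it gives 1.00.

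**Step 5: other missingness patterns** (binary confounder, OR 0.33). With 10% missing in experienced and 40% in naïve subjects, the rule gives 0.91 and complete case 1.00. With missingness of 10% or 40% by level of the confounder itself, the rule gives 0.90 and complete case 1.00.

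**Step 6: effect on inference at 150 versus 150.** For a continuous outcome with the binary confounder worth −0.5 SD (4,000 runs), the false-positive rate under the rule is 5.4%, 5.1%, 9.1% and 15.0% at 0%, 10%, 30% and 50% missing. For the logistic model with the inputs of step 2 (3,000 runs) it is 4.8%, 5.1% and 7.6% at 0%, 10% and 30%.

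**The case against.** The strongest defence is that the study is descriptive. The ENCePP checklist (Annex 2) says that no formal hypothesis is tested. The primary objective is answered by per-arm summaries that need no covariate adjustment, and evaluation within subgroups is also planned. Section 9.9 calls the extent of missing data unpredictable, not large, and sections 9.6 and 9.8 provide completeness checks and queries. At 10% missing the bias is small and the false-positive rate hardly moves. All of this stands and limits the severity. It does not rescue the rule: the adjusted comparisons are planned, and section 9.5 bases its power statement on the naïve versus experienced contrast.

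A reader might infer more than the protocol supports:

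- **That every adjusted comparison is biased.** It is not. The covariate must be incomplete, prognostic and imbalanced. Age is a poor example, since year of birth is collected without the as-available qualifier and age is an inclusion criterion.
- **That the rule breaks the outcome analyses.** Binary logistic regression has no third outcome level, and a mixed model for CD4 has no missing level, so the rule could not be applied there. But section 9.7 never says that it should be. Keeping values in multivariate analyses most naturally describes covariates, and mixed models use the observed outcomes without imputation. One can calculate that a true 92% suppression would appear as 83%, 74% or 64% (0.92 × 0.9, 0.8 or 0.7) if missing tests counted as not suppressed. That is the ordinary missing=failure estimate and no consequence of the written rule. Section 9.5 itself attributes the lower week-96 reference rates to missing data.
- **That continuous covariates must be cut into categories.** The wording invites this but does not require it, because an indicator beside a continuous term also meets it. Tertiles alone give an OR of 1.09 to 1.12 in the step 2 scenario with nothing missing. That part is due to coarse categorisation, which the protocol does not prescribe, so it is left out of the figures above.

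**Conclusion.** The point holds in limited form. The protocol forbids imputation and prescribes a method that leaves residual confounding in non-randomised comparisons whenever an adjusted covariate is incomplete, prognostic and imbalanced. This is a fixed choice and no detail left to the SAP.

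Under the assumed 0.8 SD imbalance and OR of 2 per SD, a true OR of 1.00 becomes about 1.06 to 1.07 at 10% missing and 1.18 to 1.20 at 30%. The alternative binary scenarios give 0.95 to 0.97 and 0.85 to 0.91 at the same rates. The actual size cannot be known from the protocol. The unclear scope of the sentence is a secondary wording defect. Severity: should be fixed; the descriptive primary results do not depend on it.

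**What to change.** Replace the sentence in section 9.7 with three provisions:

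1. **Baseline covariates.** Handle incomplete covariates by multiple imputation, with an imputation model that includes the outcome and the naïve/experienced group. Keep continuous covariates continuous. Leave the number of imputations and the algorithm to the SAP.
2. **Sensitivity analyses.** Report complete-case and missing-category analyses beside the main one.
3. **Outcomes.** State that the covariate rule does not apply to them. Mixed models use all observed CD4 and patient-reported values. HIV-1 RNA suppression is reported both as missing=failure and as missing=excluded, each labelled as such.

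The cost is protocol and SAP wording and some extra programming, with no new data. The downside is reliance on a missing-at-random assumption, which is open to doubt for tests recorded only when available. The complete-case analysis is a useful check here: in step 5 it stayed unbiased when missingness depended on the confounder itself, although it loses the subjects whom the present rule was meant to keep.

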9.8. Quality Control

The electronic data entry system will contain automatic checks for data completeness and to identify inconsistent data and respective queries will be generated when necessary. Data and queries will be remotely monitored for consistency and completeness.

9.9. Limitations of the Research Methods

As documentation of study variables is not obligatory missing data of unpredictable extent can occur.

Depending on the selection of sites selection bias cannot be excluded.

9.10. Other Aspects

9.10.1. Joint Investigator/Sponsor Responsibilities

9.10.1.1. Access to Information for Monitoring

The study monitor is responsible for routine remote review of the eCRFs at regular intervals throughout the study to verify the completeness and consistency of the data being entered on the forms.

Onsite monitoring visits can also be done at selected sites. For such onsite monitoring visits the investigator will provide the study monitor with access to any subject records needed to verify the entries in the eCRF. The investigator agrees to cooperate with the study monitor to ensure that any problems detected in the course of these monitoring visits are resolved.

9.10.1.2. Study Discontinuation

Both the sponsor and the investigator reserve the right to terminate the study at any time. Should this be necessary, both parties will arrange discontinuation procedures and notify the appropriate regulatory agencies and IECs. In terminating the study, Gilead and the investigator will assure that adequate consideration is given to the protection of the subjects' interests.

10. PROTECTION OF HUMAN SUBJECTS

10.1. Good Pharmacoepidemiology and Pharmacovigilance Practices

Gilead will ensure that this study is conducted in accordance with the principles of the International Conference on Harmonization (ICH) Pharmacovigilance Planning E2E guidelines, and with the laws and regulations of the country in which the research is conducted.

The investigator will conduct this study in accordance with the guidelines of Good Pharmacoepidemiology Practices (GPPs), Heads of Medicines Agencies (HMA) Good Pharmacovigilance Practices (GVP) including archiving of essential documents.

10.2. Independent Ethics Committee (IEC) Review

The investigator (or sponsor) will submit this protocol and any accompanying material to be provided to the subject (such as subject information sheets, or descriptions of the study used to obtain informed consent) to an IEC. The investigator will not begin any study subject activities until approval from the IEC has been documented and provided as a letter to the investigator.

Any subsequent modifications made to the protocol or any accompanying material to be provided to the subject after initial IEC approval will also be submitted for IEC approval prior to use, with the exception of those necessary to reduce immediate risk to study subjects.

10.3. Informed Consent

The investigator is responsible for obtaining written informed consent from each individual participating in this study after adequate explanation of the aims, methods, objectives, and alternatives of the study prior to study participation and before performing any study-related activities. The investigator must utilize the most current IEC approved consent form for documenting written informed consent. Each informed consent form will be appropriately signed and dated by the subject or the subject's legally authorized representative and the person conducting the consent discussion, and also by an impartial witness if required by IEC or local requirements.

10.4. Confidentiality

The investigator must assure that subjects' anonymity will be strictly maintained and that their identities are protected from unauthorized parties. Only a unique identifier (as allowed by local law) and a unique study identification code should be recorded on any study-related document.

The investigator agrees that all information received from Gilead, including but not limited to this protocol, CRFs, and any other study information, remain the sole and exclusive property of Gilead during the conduct of the study and thereafter. This information is not to be disclosed to any third party (except employees or agents directly involved in the conduct of the study or as required by law) without prior written consent from Gilead. The investigator further agrees to

take all reasonable precautions to prevent the disclosure by any employee or agent of the study site to any third party or otherwise into the public domain.

11. MANAGEMENT AND REPORTING OF SAFETY INFORMATION

This study will collect related adverse events (also known as adverse drug reactions, ADRs), related serious adverse events (also known as serious adverse drug reactions, SADR), and special situation reports (SSRs); general definitions and means of reporting of subsets of events are described hereafter. ADRs, SADR and SSRs will be collected for all ARV drugs used during the study.

The collection of ADR/SADR reflects the real life situation, in which the treating physician with best knowledge of his patient assesses whether an observed event could be related to a given treatment. In this way, the study will collect safety data that is reflective of the real life setting in which it is conducted.

11.1. Adverse Events

An **adverse event** (AE) is any untoward medical occurrence in a clinical study subject administered a pharmaceutical product, which does not necessarily have a causal relationship with the treatment. An AE can therefore be any unfavorable and/or unintended sign, symptom, or disease temporally associated with the use of a medicinal product, whether or not considered related to the medicinal product. AEs may also include lack of efficacy, overdose, drug abuse/misuse reports, or occupational exposure. Preexisting events that increase in severity or change in nature during or as a consequence of participation in the study will also be considered AEs.

An AE does not include the following:

- Medical or surgical procedures such as surgery, endoscopy, tooth extraction, and transfusion. The condition that led to the procedure may be an AE.
- Situations where an untoward medical occurrence has not occurred (eg, hospitalization for elective surgery, social and/or convenience admissions)
- Any medical condition or clinically significant laboratory abnormality with an onset date before the consent form is signed. These are considered to be preexisting conditions and should be documented on the medical history CRF (if applicable).

11.1.1. Adverse Drug Reactions /Serious Adverse Drug Reactions

An **adverse drug reaction** (ADR) is defined as an untoward medical occurrence (unintended or noxious responses) considered causally related to an investigational or approved medicinal product at any dose administered. Adverse reactions may also arise from medication errors, uses outside what is foreseen in the protocol or in prescribing information (off-label use), misuse and abuse of the product, overdose, or occupational exposure. ADRs which meet the criteria for a serious adverse event (see below) are defined as **serious adverse drug reaction** (SADR).

11.1.2. Serious Adverse Events

A **serious adverse event** (SAE) is defined as an event that, at any dose, results in the following:

- Death
- Life-threatening (Note: The term “life-threatening” in the definition of “serious” refers to an event in which the subject was at risk of death at the time of the event; it does not refer to an event that hypothetically might have caused death if it were more severe.)
- In-patient hospitalization or prolongation of existing hospitalization
- Persistent or significant disability/incapacity
- A congenital anomaly/birth defect
- A medically important event or reaction: such events may not be immediately life-threatening or result in death or hospitalization but may jeopardize the subject or may require intervention to prevent one of the other outcomes constituting SAEs. Medical and scientific judgment must be exercised to determine whether such an event is a reportable under expedited reporting rules. Examples of medically important events include intensive treatment in an emergency room or at home for allergic bronchospasm; blood dyscrasias or convulsions that do not result in hospitalization; and development of drug dependency or drug abuse. For the avoidance of doubt, infections resulting from contaminated medicinal product will be considered a medically important event and subject to expedited reporting requirements.

Clarification of Serious Adverse Events

- Death is an outcome of an AE, and not an AE in itself. Therefore, if death occurred, the event that led to death needs to be reported as an SAE.
- Complications that occur during hospitalizations are AEs. If a complication prolongs the hospitalization, is life-threatening, or meets any of the other definitions of an SAE, then it is an SAE.
- “In-patient hospitalization” means the subject has been formally admitted to a hospital for medical reasons, for any length of time. This may or may not be overnight. It does not include presentation and care within an emergency department.
- The investigator should attempt to establish a diagnosis of the event on the basis of signs, symptoms, and/or other clinical information. In such cases, the diagnosis (and not the individual signs/symptoms) should be documented as the AE and/or SAE.

A distinction should be drawn between seriousness and severity of AEs. Severity is a category utilized for rating the intensity of an event; both AEs and SAEs can be assessed for severity. An AE is defined as “serious” when it meets one of the predefined outcomes described above.

